1. **Study Purpose.** The primary purpose of this study is to experimentally evaluate two different comprehensive training models to train opioid treatment centers in an evidence-based behavioral treatment called contingency management (CM), which is the provision of motivational incentives for reaching specific treatment benchmarks. An exploratory goal of this study is to test whether theorized mechanisms of change – implementation climate and leadership engagement – mediate the effect of implementation condition on outcomes. Conduct of this study will address critical public health needs by (a) informing how CM, an evidence-based practice, should be implemented in OUD treatment centers, (b) improving the outcomes of OUD patients receiving treatment in the community, and (c) advancing knowledge about why and how implementation strategies work.
2. **Overview of Study Design.** A Type 3 Hybrid Trial will be conducted collecting data on both implementation and patient outcomes. We will use a 3-cohort staggered cluster RCT design. The unit of randomization will be opioid treatment centers. Centers will receive one of two comprehensive training conditions: the standard training provided by the New England Addiction Technology Transfer Center (ATTC training) or an enhanced condition that also provides leadership coaching and provider incentives (E-ATTC training). The primary research activities will be measuring the effectiveness of the training initiatives by gathering data from organizations, providers and patients.

Every 12-16 months, 10 OUD centers will be randomly selected to initiate study activities (10 centers X 3 cohorts = 30 centers). Prior to randomization, each center will complete a Baseline Organizational Assessment (described further in the Measures section) to collect organizational background data (e.g., years in operation, number of patients served annually, number of staff, medications prescribed, implementation readiness). Using these data, urn randomization procedures (balancing on number of patients served and percent of patients receiving methadone) will be used to randomize centers to either the ATTC or the E-ATTC condition. Centers in both conditions will complete a 5-month Preparation phase, a 9-month Implementation phase, and a 12-month Sustainment phase (26 months total). In both conditions, providers will record their delivery of CM in the electronic medical record and will audio record one CM session per month.

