one of three trained CM staff will turnover during the project's first two phases, each center will be required to identify one or more replacement CM staff. Thus, if one of the initially trained CM staff withdraws from the study for any reason during the Preparation or Implementation phase, a replacement CM staff will be immediately trained.

- c. *Community-based OUD treatment center patients (Patients).* Each center will agree to deliver CM to all patients newly admitted over a 6-month period. In addition, each center will be asked to enroll approximately one eligible CM patient per week to complete research assessment measures. Eligible patients will be: a) adult patients, b) newly admitted to the opioid treatment center within the past 30 days, and c) prescribed any FDA-approved OUD medication. To optimize ecological validity, exclusion criteria will be minimal and will only include issues that could interfere with the ability to complete a brief intake interview including acute intoxication, acute psychosis, acute mania, or cognitive impairment (prohibiting comprehension of the consent process), as reported by opioid treatment center staff or observed by research staff. We focus on newly admitted patients as opposed to those established in treatment because the need is highest among these patients: drop-out rates and missed doses are higher during the first 6 months of treatment (i.e., the "induction phase") than any subsequent period.

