In other weeks, patients at Organization B might have 3 clinical contacts expected (e.g., 1 medication dose, 1 urine screen, 1 counseling session). In these weeks, a patient who presented for only buprenorphine would have the following compliance rate: 1 actual visit / 3 expected visits = 33%, and would not receive a prize draw. Likewise, a patient that presented for only buprenorphine and a counseling session but missed the urine screen would have the following rate: 2 actual visits / 3 expected visits = 66%, and would not receive a draw. Patients would have to attend all 3 clinical contacts to receive a prize draw.

[figure not shown]
The CM protocol that staff will be trained in will consist of the following actions: 1) Review patient compliance for the week with patient using the organization definition of number of expected clinical contacts; 2) Clearly inform the patient if their compliance for week exceeded the organizational CM benchmark; 3) Clearly state the number of prize draws (if any) earned in the current session; 4) Administer CM prize draws as appropriate; 5) State number of draws patient can earn at the next session (goal-setting); 6) Praise patient's efforts towards compliance (even if the compliance benchmark was not met); and 7) Communicate confidence that patient's efforts will yield success in the future.

The evidence-based CM protocol⁶⁻⁸ that staff will be trained in will provide patients with increasing opportunities for winning cost-neutral (i.e., praise), \$1, \$20, and \$100 prizes for each week during which the CM compliance benchmark was attained. Draws increase by one for each week that compliance was attained. Failure to attain the benchmark or failure to attend the prize draw session resets draws for the next week down to one, with draws again escalating for sustained compliance. Patients will receive prize draws for up to 12 weeks, which is the median duration of the induction phase at participating centers (range

from 4 to 26 weeks). This progression will yield a maximum of 78 draws ($1+2+3+\dots+12$). Fishbowls will contain 500 slips; 250 state “good job!” but are not associated with a prize, 209 state “small,” 40 state “large,” and one “jumbo.” Using these probabilities and magnitudes of \$1, \$20, and \$100 for the three respective prize sizes, each draw has an average cost of \$2. Thus, for a 12-week protocol, each patient could earn 78 draws \times \$2/draw = \$156 in prizes.

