Incentive amounts are designed to enable staff to, on average, earn bonuses that during a 12-month period would comprise about 6% of their mean annual base salary of US \$45,000. Prior P4P research^{18,19} has suggested that bonuses between 4 and 7% are large enough to significantly improve staff performance, yet modest enough to be practical for community treatment centers to implement. Provision of incentives will follow the exact same schedule of provision of performance feedback reports described in 7a. Sessions must be submitted by the last day of the month and must be from that calendar month. Within 2-4 weeks following submission of recordings, providers in the E-ATTC condition will receive email notifications from research staff containing their performance feedback reports, as well as confirmation of their achievement of CM Exposure and CM Competence for the prior month. CM staff enrolled in the E-ATTC condition will receive payments via cash, check, or Clincard.

8. Data Collection Procedures.

- a. *Organizational background form.* Prior to randomization, leaders at each center will collaboratively complete an Organizational Background Form via Qualtrics. Data collected will include, but not be limited to: number of patients, proportion of patients on different OUD medications, number of staff, average staff tenure, and years in operation.
- b. *Staff surveys.* After randomization, CM staff and leadership staff will complete two online Qualtrics surveys: one at the start of the Preparation phase and one at the midpoint of the Implementation phase. The first survey (30-45 minutes) will contain the following measures: Provider Demographics, Organizational Readiness for Change, Attitudes towards CM, and putative mediators (i.e., Implementation Climate, Leadership Engagement). The second survey (15-30 minutes) will only evaluate the putative mediators. Participating staff will receive \$25 for the first and \$20 for the second survey. We attained 82% or higher completion rates on comparable staff follow-up surveys in the New England ATTC pilot.

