- e. *Audio recordings of CM sessions*. CM staff in both implementation conditions will be required to submit audio recordings of CM sessions once per month in order to receive performance feedback and P4P incentives. Submissions will be made using the Brown CIS recommended solution of Virtru encrypted email. A Brown research staff member will email each site a reminder that audio recordings are due using Virtru encrypted email: as long as providers reply to this email, audio recordings will be encrypted. Use of Virtru will be demonstrated during both the upfront didactic training and the ongoing monthly coaching calls.

9. Key Measures.

- a. *Implementation outcomes*. Our **Primary Aim** tests the effectiveness of the two implementation conditions (ATTC vs. E-ATTC) on CM Exposure, CM Competence, and CM Sustainment.
 - i. **CM Exposure**. This is a patient-level measure of the number of CM sessions delivered per patient during the 9-month Implementation phase. As described above, at each site, data will be extracted from the medical record (by center staff blind to condition) and entered into the Medical Record Data Extraction Form for the 25 patients enrolled in the study (25 patients * 30 sites = 750 patients) at the end of the Implementation phase. A Medical Record Data Extraction form will be filled out for every Self-Report Data Form completed in the patient medical record. Based on empirically derived benchmarks from prior RCTs,¹⁰ 10 or more complete CM sessions per patient (out of a maximum of 24) is the target level of CM Exposure to merit P4P incentives. To reach the target level of CM Exposure for a given patient, at least 10 Medical Record Data Extraction forms must be completed.
 - ii. **CM Competence**. This is a staff-level measure of staff's skill in CM delivery during the 9-month Implementation phase. Each month, CM staff will submit audio-recordings, one of which will be randomly selected for rating by coders blind to implementation condition using the CM Competence Scale¹² (CMCS). The scale contains 9 items scored from 1 to 7, with 7 denoting excellent competence. Based on empirically derived benchmarks from prior RCT research,¹³ an average CMCS score of 5.8 across items is the target to earn P4P incentives. A continuous measure of CMCS scores will be created for each staff on a monthly basis.

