 - iii. **CM Sustainment**. This is a patient-level measure of the number of CM sessions delivered per patient during the 12-month Sustainment phase. Using the same protocol as for CM Exposure, data will be extracted at the end of the Sustainment phase from 25 randomly selected patients meeting eligibility criteria (i.e., newly admitted to OUD pharmacotherapy during the Sustainment phase; 25 patients * 30 sites = 750 patients). A continuous measure of the number of sessions received, as counted by the number of Medical Record Data Extraction forms completed, will be created for each patient.

b. *Patient outcomes.* Our **Secondary Aim** tests the effectiveness of the two implementation conditions (ATTC vs. E-ATTC) on two patient outcomes: Opioid Abstinence and Opioid-Related Problems.

- i. **Opioid Abstinence.** Patient abstinence from opioids will be assessed via 3- and 6-month post-baseline interviews, during which patients will self-report days of abstinence using the Timeline Followback (TLFB).²⁰ Abstinence will be corroborated via dip urine screens from Redwood Toxicology testing for: heroin/opiates, oxycontin, benzodiazepines, cocaine, methamphetamines, and THC. In addition, at the request of participating centers, single-panel screens will test for fentanyl, a highly lethal opioid not detected in multi-panel screens. A urine screen negative for all opioids (heroin/opiates, oxycontin, fentanyl) will be required for coding of 90 days abstinence. Other drug use detected via the TLFB or urine will be examined as covariates in the analysis.
- ii. **Opioid-Related Problems.** Opioid-related problems will be assessed via patient self-report at 3- and 6-months post-baseline using the Substance Problem Index,²¹ which is a count of DSM symptoms experienced by the patient (range from 0 to 11). Both Drs. [name] and [name] have successfully used this index²²⁻²⁴ in prior studies. The index will be tailored to focus specifically on problems due to opioids.

c. *Putative mediators.* Our **Exploratory Aim** tests putative mediators of implementation outcomes: implementation climate and leadership engagement. Organization-level scoring is described in **Analytic Plan**. The putative mediator scales are measured at the start of the Preparation phase and the midpoint of the Implementation phase.

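### As planned, the mediation analysis does not separate mediation from reverse effects for CM Exposure, CM Competence and 3-month patient outcomes

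*Combined protocol and SAP*

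**What the plan says.** Section 8.b (Staff surveys) schedules two surveys after randomization, "one at the start of the Preparation phase and one at the midpoint of the Implementation phase", and section 9.c (Putative mediators) repeats that timing for implementation climate and leadership engagement: "The putative mediator scales are measured at the start of the Preparation phase and the midpoint of the Implementation phase".

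The outcomes these mediators are meant to explain have different windows:

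- CM Exposure (9.a.i) is the "number of CM sessions delivered per patient during the 9-month Implementation phase".
- CM Competence (9.a.ii) is a monthly score on the CM Competence Scale (CMCS) over the same 9 months.
- CM Sustainment (9.a.iii) counts sessions for patients newly admitted in the later 12-month phase.
- Opioid abstinence and opioid-related problems (9.b) are assessed at 3 and 6 months.

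The Exploratory Hypothesis (Specific Aims) covers every one of these outcomes. Section 10.c regresses the outcome on condition, then on condition and mediator, and takes the change in the condition coefficient as the mediated effect. It does not say which survey supplies the mediator, does not adjust for the start-of-Preparation score, and does not limit any outcome to the period after the survey. The covariate list in 9.d does not include the early mediator scores either.

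Two further statements fix the timing of delivery. In section 3.c each center is to "deliver CM to all patients newly admitted over a 6-month period", and section 5 states: "Patients will receive prize draws for up to 12 weeks".

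**The concern.** A mediator should come before the outcome it explains. The start-of-Preparation survey precedes the bonuses and almost all of the coaching, so it can serve as a baseline but not as the mediator. That leaves the midpoint survey, which CM Exposure and CM Competence straddle.

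A reverse path is plausible in this trial. The climate scale asks, among other things, how far the center rewards CM. Under section 7.b, E-ATTC providers earn $200 for each patient who reaches 10 sessions and $50 for each month of competent delivery. Ten weekly sessions take 10 × 12/52 = 2.3 months, so the first Exposure bonuses can be earned and confirmed before month 4.5. Successful early delivery may therefore lift the ratings, and do so more in one arm. A difference-in-coefficients method would count that as mediation.

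What is at stake is the trial's stated purpose of learning why and how implementation strategies work, which rests on this aim.

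**Working it through.** **The plan's own timeline.** 5 + 9 + 12 = 26 months, as stated in section 2. The Implementation midpoint is 9/2 = month 4.5 of that phase, or 5 + 4.5 = month 9.5 of the study.

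**CM Exposure.** The documents give 6 months of admissions (3.c), up to 12 weeks of CM (5) and a 9-month count (9.a.i). I assume even admission from the first day of Implementation and evenly spaced sessions.

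- Course length: D = 12 × 12/52 = 2.77 months.
- A patient admitted at month e has the share min(D, max(0, 4.5 − e))/D of sessions before the survey.
- Patients admitted before 4.5 − 2.77 = 1.73 have all their sessions before it. Those admitted between 1.73 and 4.5 have a falling share, averaging one half. The rest have none.
- Mean share: (1.73 + 2.77/2)/6 = 3.115/6 = **52%**.
- Patients who have finished CM by the survey: 1.73/6 = **29%**.

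The assumed start is close to forced if every patient is to get 12 weeks within the phase: 6 + 2.77 = 8.77 of 9 months, leaving 0.23 month of slack. A later start would lower the share.

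The maximum of 24 sessions in 9.a.i could mean twice weekly for 12 weeks or weekly for 24 weeks; the documents do not say. Sessions are cut off at month 9 below.

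| Admission period | 12 weeks of CM | 24 weeks of CM |
|---|---|---|
| 6 months | 51.9% | 33.7% |
| 25 weeks (25 patients at about one per week) | 54.0% | 34.6% |
| 9 months | 40.9% | 29.3% |

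**CM Competence.** The midpoint falls within the fifth month, so 4 or 5 of 9 monthly scores precede it: 44% to 56%.

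**CM Sustainment.** 0% precedes the survey.

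**Patient outcomes**, with even intake over 6 months and an assumed 90-day (3-month) look-back:

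- 3-month interviews before the survey: (4.5 − 3)/6 = 25%.
- Their look-back time before it: (1.5 + 3/2)/6 = 50%. For the 75% of interviews held after the survey, this is (0.50 − 0.25)/0.75 = 33%.
- 6-month interviews before the survey: none. Their look-back time before it: (1.5²/2)/3/6 = 6%.

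**Illustration of the bias.** I simulated 30 centers, 15 per arm, 2,000 times, with no true effect of the mediator on sessions. All effect sizes are assumptions: a condition effect of 0.8 in each half of the phase; a shared center factor and half-specific noise, each with SD 0.7; and a mediator equal to 0.5 or 1.0 times early sessions plus noise with SD 1. The analysis was by ordinary regression on center values.

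| Outcome analysed | Spurious mediated effect | Mediator coefficient significant |
|---|---|---|
| Whole phase | 0.12 to 0.30 | 55% to 96% |
| After the midpoint only | 0.08 to 0.19 | 21% to 46% |
| After the midpoint, adjusted for earlier sessions | about 0.00 | 4% to 5% |

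The whole-phase artefact is 0.12/0.8 = 15% to 0.30/0.8 = 38% of the assumed condition effect. The planned Freedman–Schatzkin statistic rejected in 34% to 75% of whole-phase runs. In the adjusted analysis it still rejected in 7% to 12%, but I computed it with the unadjusted correlation between condition and mediator, so that last figure is not a clean guide. The start-of-Preparation score was not part of the simulation.

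**The case against.** The best defence is that the design already holds most of what is needed. There is a mediator survey before Implementation, competence is scored monthly, and one extraction form is completed per session. CM Sustainment lies wholly after the midpoint survey, and 6-month outcomes almost wholly. A reader might infer that the survey schedule makes mediation untestable, or that much of every outcome precedes the mediator. Neither follows: the schedule can support an ordered analysis for several outcomes, and the gap lies in the model.

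A second defence concerns the bonuses. They are part of E-ATTC, so climate ratings raised by being paid are at least partly the hypothesised path from condition to mediator. Because bonuses start in Implementation, a mid-phase survey is a reasonable compromise. This stands, but it does not help with whole-phase outcomes: the bonus follows delivery that is itself counted in the outcome.

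Third, simply cutting the outcome at the survey is not a remedy. It would give zero sessions by construction to the 29% of patients who had finished, and it leaves early delivery as a common cause of ratings and later delivery. The start-of-Preparation score predates all delivery and cannot block that path. This stands and shapes the fix.

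Finally, the 52% depends on assumed accrual and session spacing. That is so, but in the scenarios above the share does not fall below 29%.

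**Conclusion.** The point holds for CM Exposure, CM Competence and 3-month patient outcomes: as written, section 10.c would let early delivery count as mediation. About 52% of Exposure sessions precede the survey under even 6-month admission and 12 weeks of CM, with a range of 29% to 54%. The simulation shows that the bias can be material under its assumptions; it does not estimate its size in this trial.

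For CM Sustainment and 6-month outcomes the time order is right, and what remains is possible confounding by earlier delivery.

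A reader might also infer that sessions can readily be split at the survey date. The documents do not show this. Recordings are tied to a calendar month (7.a), but no session date field is described, and Implementation-phase records are extracted once, at the end of that phase (8.d).

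The matter is minor in rank. The aim is exploratory, and the primary and secondary comparisons of condition are untouched.

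**What to change.** Amend the Exploratory Aim in section 10.c:

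1. Name the midpoint survey as the mediator and adjust for the start-of-Preparation score.
2. Make CM Sustainment the leading mediation outcome, with the 6-month outcomes for patients.
3. For CM Competence, use the monthly CMCS scores after the survey, adjusted for those before it.
4. Adjust all models for the center's CM delivery before the survey. Section 7.a says that monthly feedback in both conditions covers exposure, so running counts may exist; this should be confirmed. If they do not, the report should say that this adjustment was not possible.
5. For CM Exposure, if session dates can be retrieved, model post-survey sessions with an offset for each patient's remaining CM time. Otherwise report the whole-phase result as an association, not as mediation.
6. Treat 3-month outcomes assessed before the survey as associations in the same way, and note that the later 3-month interviews still look back partly across it.

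The variance used in the Freedman–Schatzkin statistic should reflect the added covariates.

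Costs: no new visits or instruments, but fewer observations and less precision. The restricted Exposure measure differs from the primary outcome definition and leaves out patients with no CM time remaining, so it does not cover the full intent-to-treat set. Early delivery is itself affected by condition, so adjusting for it also removes any genuine mediation that worked through delivery before the survey. The adjusted result should be described as mediation of later delivery, given earlier delivery.
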